## 6.4.4. Change from baseline to Day 302 in CHOP INTEND total score: comparison: 50/28mg versus 12 mg Group from 232SM203.

### Main Analysis

• The change from baseline to Day 302 in CHOP INTEND total score will be analyzed using the JRT methodology to account for mortality.

### Sensitivity Analyses

- In order to test sensitivity of data handling for withdrawals not due to death, ranking criteria will be adjusted in the JRT for withdrawals not due to death.
- In order to test if permanent ventilation should be considered in evaluation of endpoint, ranking criteria will be adjusted for JRT to consider permanent ventilation in evaluation.
- The MI model will be run for total score for the ITT population excluding data from any subjects who died.
- Rank based implementation of joint rank method + MI.
- The main analysis will be repeated incorporating Jump to reference in the MI step.
- The main analysis will be repeated using PPS set.

### Supplementary analyses

o ANCOVA

Product: Nusinersen	Statistical Analysis Plan
Study: 232SM203	Version: 3.0 Final

for more details section 6.3.

## Table 9: Change from baseline to Day 302 in CHOP INTEND total score comparison:50/28mg versus 12 mg Group from 232SM203

Туре	Analysis Method	Analysis Population: Further Notes
Main analysis	Joint rank using multiple imputation (MI)	ITT Set
Sensitivity analysis	Adjustment of ranking criteria for JRT for withdrawals not due to death	ITT Set
	Adjustment of ranking criteria for JRT for permanent ventilation	ITT Set
	Subjects who died will be excluded from the MI model	ITT Set
	Rank based implementation of joint rank method + MI	ITT Set
	Joint rank using multiple imputation (MI)	PPS Set
	Main analysis repeated using Jump to reference in the MI step	ITT Set
	Joint rank using multiple imputation (MI)	ITT Set
	by disease duration	
	Log-rank test stratified by disease duration at Screening; by baseline CHOP INTEND	ITT Set
		Analysis

Endpoint and Comparison	Analysis Method	Analysis Population: further notes
Supplemental analysis		
Difference (50/28mg- 12 mg Group from 232SM203) in change in	ANCOVA using MI	ITT Set

CHOP INTEND from baseline by visit

## 6.4.5. Change from baseline to Day 302 in HINE Section 2 motor milestones total score: comparison: 50/28mg versus 12 mg Group from 232SM203.

### Main, sensitivity and supplementary analyses

Main, sensitivity and *supplementary* analyses will be analyzed in the same way as similar secondary endpoint described in 6.4.4.

## Table 10: Change from baseline to Day 302 in HINE Section 2 motor milestones totalscore: comparison: 50/28mg versus 12 mg Group from 232SM203

Туре	Analysis Method	Analysis Population: Further Notes
Main analysis	Joint rank using multiple imputation (MI)	ITT Set
Sensitivity analysis	Adjustment of ranking criteria for JRT for withdrawals not due to death	ITT Set
	Adjustment of ranking criteria for JRT for permanent ventilation	ITT Set
	Rank based implementation of joint rank method + MI	ITT Set
	Main analysis repeated using Jump to reference in the MI step	ITT Set
Endpoint and Comparison	Analysis Method Pe	nalysis opulation: rther notes

### Supplemental analysis

Difference (50/28mg- 12	ANCOVA using MI	ITT Set
mg Group from		
232SM203) in change in		

Product: Nusinersen Study: 232SM203

HINE section 2 from baseline by visit

## 6.4.6. Change in Plasma NF-L from (ratio to) baseline to Day 64: comparison: 50/28mg versus 12 mg Group from 232SM203.

### Main and sensitivity analyses

The analysis will be performed on the ITT set but is it noted that neurofilament plasma samples from China sites were not analyzed due to export law complication. The baseline and post baseline results for NF-L for these participants will be imputed in the MI step.

Main and sensitivity will be analyzed in the same way as described in section 6.4.3.

### Supplementary analyses

• Population level summary – ANCOVA

### Table 11: Change in Plasma NF-L from (ratio to) baseline to Day 64: comparison: 50/28mg versus 12 mg Group from 232SM203.

Туре	Analysis Method	Analysis Population: Further Notes
Main analysis	Joint rank using multiple imputation (MI)	ITT Set
Sensitivity analysis	Adjustment of ranking criteria for JRT for withdrawals not due to death	ITT Set
	Rank based implementation of joint rank method + MI	ITT Set
Endpoint and Comparison	Analysis Method	Analysis Population: further notes
Supplemental analysis		

. .

Product: Nusinersen	Statistical Analysis Plan
Study: 232SM203	Version: 3.0 Final

Difference (50/28mg- 12 mg Group from 232SM203) in change in Plasma NF-L from baseline by visit	ANCOVA using MI	ITT Set
by visit		

## 6.4.7. Time to death or permanent ventilation (≥ 16 hours ventilation/day continuously for > 21 days in the absence of an acute reversible event, or tracheostomy): comparison: 50/28mg versus CS3B sham control

Permanent ventilation is defined as tracheostomy or  $\geq 16$  hours of ventilation/day continuously for  $\geq 21$  days in the absence of an acute reversible event (Appendix B). Note that it was originally planned to include additional follow-up data from extension study in the analysis, but in order to focus this analysis plan on 232SM203 this will now be analyzed as part of the integrated 232SM203/232SM302 analysis plan.

An independent endpoint adjudication committee (EAC) will determine, in a blinded fashion, the date at which a participant is considered to have met the definition of an event. The procedures for reviewing and adjudicating event will be described in a charter.

The main analysis is to compare the time to death or permanent ventilation between the two treatment groups with the log-rank test stratified by disease duration at Screening (<=12 weeks or >12 weeks). Only events that were adjudicated by the EAC as meeting the protocol defined criteria for permanent ventilation or death will be included in the main analysis. Participants who do not meet the endpoint definition will be censored on the last occasion the participant was seen (either in-person visit or by telephone contact), irrespective of whether the participant has completed the full course of treatment and whether the participant has completed the study or permanently withdrawn. The exception is time to death or permanent ventilation cases in which a participant has begun a ventilator diary, in which case the latest entry in the diary will be used as the date of censoring.

Kaplan-Meier estimates of the cumulative probability of the time to death or permanent ventilation over time will be determined for the ITT population. Treatment comparisons of time to death or permanent ventilation will be based on a stratified log rank test. Stratification factor will be disease duration at Screening (<=12 weeks or >12 weeks). Kaplan-Meier plots will be presented. The median time to death or permanent ventilation, percentiles (5th, 10th, 25th, 75th,

Product: Nusinersen	Statistical Analysis Plan
Study: 232SM203	Version: 3.0 Final

90th) and associated 95% confidence limits, and proportion of subjects who meet an event by fixed time points (i.e. Day 183 and Day 302) will be estimated using Kaplan-Meier.

The start date for calculating time to death or permanent ventilation in days i.e. death, permanent ventilation or censoring will be date of first dose. If a subject is adjudicated as having an event, the date they were considered to meet the endpoint either death or reach the definition of permanent ventilation will be provided as part of the adjudication.

The proportion of subjects meeting the endpoint of time to death or permanent ventilation will be presented by treatment group. For subjects who met the endpoint the number of days per subject at which ventilation use was at least 16 hours per day will be summarized.

### Main analysis

Log-rank test stratified by disease duration at Screening.

### Sensitivity Analyses

- The main analysis will be repeated using the actual treatment assignment. If participant, randomized to 12 mg nusinersen, receives 50 or 28 mg nusinersen at any point during the study, then the participant will be counted in the 50 mg nusinersen group.
- The treatment groups will be compared using a Cox proportional hazards model for time to death or permanent ventilation, adjusted for each subject's disease duration at Screening (rather than the binary stratification factor, ≤ 12 weeks/ > 12 weeks) and baseline CHOP INTEND total score. Only events that were adjudicated by the EAC will be included in this sensitivity analysis. This analysis allows estimation of a hazard ratio of nusinersen relative to the CS3B sham with its associated 95% confidence intervals.
- The main analysis will be repeated for the following subgroups: disease duration and Baseline CHOP INTEND

 Table 12: Time to death or permanent ventilation: comparison: 50/28mg versus CS3B

 sham control

Туре	Analysis Method	Analysis Population: further notes
Main Analysis	Log-rank test stratified by disease duration at Screening	Matched Sham Set

Product: Nusinersen Study: 232SM203		Statistical Analysis Plan Version: 3.0 Final
Sensitivity Analysis	Cox proportional hazards with treatment and each subject's disease duration at Screening and baseline CHOP INTEND total score as terms in the model	Matched Sham Set
	Log-rank test stratified by disease duration at Screening; by disease duration at Screening	Matched Sham Set
	Log-rank test stratified by disease duration at Screening; by baseline CHOP INTEND	Matched Sham Set

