## 2.2. Study Design

This 3-part study will evaluate the efficacy and safety of a high dosing regimen of nusinersen in approximately 145 participants. The study will be conducted at approximately 65 sites globally. Following the completion of this study, all eligible participants may elect to enrol in a separate long-term extension study (232SM302), pending study approval by ethics committees and the appropriate regulatory authorities. In regard to participants rolling over from Part B, this will be done without unblinding the participant's treatment group.

Part B will consist of a pivotal, double-blind, active-controlled treatment period with either 2 or 4 loading doses of nusinersen (for the 50/28 mg Group and Control Group, respectively) administered intrathecally followed by maintenance doses approximately every 4 months thereafter. Approximately 75 participants with infantile-onset SMA will be randomized in a 1:2 ratio to receive either the currently approved dosing regimen or a 50/28 mg dosing regimen.

In the Control Group, up to a total of 25 participants will receive 4 loading doses of 12 mg of nusinersen administered intrathecally (Days 1, 15, 29, and 64), followed by maintenance doses of 12 mg on Days 183 and 279 (and a sham procedure on Day 135).

Product: Nusinersen	Statistical Analysis Plan
Study: 232SM203	Version: 3.0 Final

In the 50/28 mg Group, up to a total of 50 participants will receive 2 loading doses of 50 mg of nusinersen administered intrathecally (Days 1 and 15) and 2 sham procedures on Days 29 and 64, followed by maintenance doses of 28 mg on Days 135 and 279 (and a sham procedure on Day 183). In order to maintain blinding sham procedures will be used as shown in the table below.

Arm	Dose 1	Dose 2	Dose 3	Dose 4	Dose 5	Dose 6	Dose 7
50/28 mg	D1	D15	D29	D64	D135	D183	D279
Group	(50 mg)	(50 mg)	(sham)	(sham)	(28 mg)	(sham)	(28 mg)
Control (12/12	D1	D15	D29	D64	D135	D183	D279
mg) Group	(12 mg)	(12 mg)	(12 mg)	(12 mg)	(sham)	(12 mg)	(12 mg)

Participants will remain at the clinic for at least 24 hours after each study treatment administration or sham procedure.

Randomization in Part B will be performed using interactive response technology (IRT) and the randomization will be stratified by disease duration as follows:

- $\leq$  12 weeks and
- > 12 weeks (time from age at symptom onset to age at informed consent)

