#### The Intent-to-Treat (ITT) Set

The Intent-to-Treat (ITT) Set is defined as all participants who are randomized and receive at least one dose of nusinersen; participants will be analyzed in the treatment group to which they are randomized. This will be the primary population for the analysis of efficacy endpoints.

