## 6.4.8. Time to death (overall survival): comparison: 50/28mg versus CS3B sham control

Overall survival will be analyzed in the same way as time to death or permanent ventilation.

Analysis Method	Analysis Population: further notes
Log-rank test stratified by disease duration at Screening	Matched Sham Set
Cox proportional hazards with treatment and each subject's disease duration at Screening and baseline CHOP INTEND total score as terms in the model	Matched Sham Set
Log-rank test stratified by disease duration at Screening; by disease duration at Screening	Matched Sham Set
Log-rank test stratified by disease duration at Screening; by baseline CHOP INTEND total score.	Matched Sham Set
	
 
Log-rank test stratified by disease duration at Screening
 
Cox proportional hazards with treatment and each subject's disease duration at Screening and baseline CHOP INTEND total score as terms in the model
 
Log-rank test stratified by disease duration at Screening; by disease duration at Screening
 
Log-rank test stratified by disease duration at Screening; by baseline CHOP INTEND total
 

Table 13: Time to death: comparison: 50/28mg versus CS3B sham control

Product: Nusinersen	Statistical Analysis Pla	
Study: 232SM203	Version: 3.0 Final	

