## 6.4.9. Time to death or permanent ventilation (tracheostomy or ≥ 16 hours of ventilation/day continuously for > 21 days in the absence of an acute reversible event): comparison: 50/28mg versus 12 mg Group from 2328M203

Main and sensitivity analyses will be analyzed in the same way as similar secondary endpoint described in section 6.4.7.

Туре	Analysis Method	Analysis Population: further notes
Main Analysis	Log-rank test stratified by disease duration at Screening	ITT Set
Sensitivity Analysis	Cox proportional hazards with treatment and each subject's disease duration at Screening and baseline CHOP INTEND total score as terms in the model	ITT Set
	Log-rank test stratified by disease duration at Screening; by disease duration	ITT Set
	Log-rank test stratified by disease duration at Screening; by Baseline CHOP INTEND	ITT Set
	Joint rank using multiple imputation (MI)	PPS Set

Table 14: Time to death or permanent ventilation: comparison: 50/28mg versus 12 mg	g
Group from 232SM203	

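### The as-treated sensitivity analysis of survival credits event-free 12 mg time to the higher dose, which on average tilts the 50/28 mg versus 12 mg comparison towards the higher dose if dosing errors occur after Day 1

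*SAP*

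**What the plan says.** All references are to the Part B infantile-onset SAP.

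- **The rule.** The first sensitivity analysis in section 6.4.7 reads "The main analysis will be repeated using the actual treatment assignment". It then states that a participant randomised to 12 mg who "receives 50 or 28 mg nusinersen at any point during the study, then the participant will be counted in the 50 mg nusinersen group". There is no limit on when the dose was given or on how many such doses are needed.
- **The clock.** Section 6.4.7 sets the start date for the time to "death, permanent ventilation or censoring will be date of first dose". Nothing restarts it at a later higher dose.
- **The test being repeated.** "Log-rank test stratified by disease duration at Screening", with groups fixed for the whole of follow-up.
- **The carry-over.** Section 6.4.8 says "Overall survival will be analyzed in the same way as time to death or permanent ventilation". Section 6.4.9, the comparison with 12 mg, says "Main and sensitivity analyses will be analyzed in the same way as similar secondary endpoint described in section 6.4.7". Section 6.4.10 refers back to 6.4.8.
- **The main analyses.** Those against 12 mg use the ITT Set, in which "participants will be analyzed in the treatment group to which they are randomized". Those against sham use the Matched Sham Set, which section 3.6.2 builds from CS3B sham participants and higher-dose participants only.
- **The tables.** Tables 12 to 15, which list the analyses for 6.4.7 to 6.4.10, have no as-treated row.

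**The concern.** Group membership is decided by something that happens after time zero, while all time since Day 1 is credited to the group so decided. A 12 mg participant wrongly given 28 mg on Day 279 has had 278 days on 12 mg, yet all of them count as higher-dose time. That participant also had to be alive on Day 279 to be moved. A comparable participant who died on Day 100 without a wrong dose stays in the 12 mg group. The rule therefore tends to take event-free follow-up out of the 12 mg group and leave the early events behind.

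The schedule in section 2.2 makes late switches the natural case. In the 50/28 mg arm, 28 mg is scheduled only on Days 135 and 279, so by naming 28 mg the rule reaches errors at those visits. A sensitivity analysis is read as a test of whether the main result survives a different assumption. If this one leans towards the higher dose on death and ventilation, its agreement with the main result is weak reassurance.

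**Working it through.** **Plan figures.** The SAP states no event count, hazard ratio or power for the time-to-event endpoints, so there is nothing of that kind to reproduce. Its only power figure (at least about 99%, section 2.3) is for the primary endpoint and has no bearing here.

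**Inputs from the SAP.** "Approximately 75 participants with infantile-onset SMA will be randomized in a 1:2 ratio": 75 × 1/3 = 25 on 12 mg and 75 × 2/3 = 50 on 50/28 mg. Visits after Day 1 are Days 15, 29, 64, 135, 183 and 279. The clock starts at first dose, and follow-up is taken to Day 302.

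**Assumed, because the SAP does not say.** Exponential event times; 60% or 80% event-free at Day 302 on 12 mg; k = 1 to 5 of the 25 control participants given a wrong higher dose, each at a visit drawn at random from Days 15 to 279.

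**Method.** A control participant is moved only if event-free on the day of the wrong dose, and then counts as higher dose from Day 1. The log-rank test is unstratified, with 20,000 runs per setting and HR = exp(Σ(O − E)/ΣV). False wins are runs with z < −1.96. Ranges cover the 80% and 60% settings.

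**Against 12 mg, true HR 1.00:**

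| Wrong doses (k) | Mean number moved | HR as randomised | HR under the rule | False wins under the rule |
|---|---|---|---|---|
| 1 | 0.83–0.92 | 1.00 | 0.98 | 3.2–3.4% |
| 2 | 1.66–1.84 | 1.00 | 0.95–0.96 | 3.9% |
| 3 | 2.50–2.75 | 1.00–1.01 | 0.93–0.94 | 4.1–4.3% |
| 5 | 4.15–4.60 | 1.00 | 0.89 | 5.3–5.9% |

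As randomised, false wins run at about 3.0%.

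**Timing drives the size (k = 2).** Both errors on Day 1 give 1.00, both on Day 15 give 0.99–1.00, and both on Day 279 give 0.90–0.91. This gradient is what immortal-time bias predicts: the longer the 12 mg time before the switch, the larger the shift.

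**With a real effect.** For a true HR of 0.7 and k = 2, the estimate moves from 0.68–0.69 as randomised to 0.65–0.66.

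**Against sham (6.4.7, 6.4.8).** The rule removes nobody from the comparator and only adds participants to the higher-dose arm. With 50 versus 20, 50% event-free on sham (assumed) and no effect, the HR moves from about 1.00 to 0.996 (k = 1), 0.985 (k = 2) and 0.967 (k = 5). With assumed HRs against sham of 0.4 (higher dose) and 0.5 (12 mg), it moves from 0.34 to 0.33 (k = 2) and to 0.32 (k = 5).

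**Direction in a single case, against 12 mg.** Start from an illustrative 10/50 versus 5/25, 20.0% in each arm. Moving one control who stays event-free gives 10/51 = 19.6% versus 5/24 = 20.8%. Moving one who has an event after the switch gives 11/51 = 21.6% versus 4/24 = 16.7%. The bias is a tendency and does not hold in every data set.

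**The case against.** The strongest case against is that little depends on this analysis. It is one sensitivity bullet, and the ranked tests 8 to 11 keep the randomised groups or the Matched Sham Set. There is no planned crossover, so reclassification needs a dosing error in a double-blind trial run through IRT. The SAP gives no error count, and with none the bias is zero. All of this stands, and it rules out some stronger readings that a reader might infer:

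- **That the survival comparison itself is biased.** The main analyses never use the rule.
- **That the rule always favours the higher dose.** The second single-case calculation goes the other way.
- **That early events can never move.** A wrong dose on Day 1 or Day 15 followed by an early event does move. For the composite endpoint the SAP section does not say that dosing stops at permanent ventilation, so being event-free before the switch is strictly required only for death. If ventilated participants are still dosed, the bias on the composite is smaller than simulated.
- **That all four endpoints are affected alike.** Participants on 12 mg are outside the Matched Sham Set, so the 19.6% versus 20.8% shift cannot arise in 6.4.7 or 6.4.8.
- **That the shift is large.** A 3% error chance at each of seven visits gives a rate ratio of about 0.91 in simulation, but it implies 1 − 0.97^7 = 19% of event-free controls misdosed, about 4.8 of 25. A 1% chance implies 1 − 0.99^7 = 7%, about 1.7 of 25, and gives about 0.98.
- **That the rule is plainly one-sided.** The bullet opens with actual treatment in general, and section 5.5 cites the long half-life, which supports keeping anyone ever exposed to the higher dose in that group. The case left open is a 50/28 mg participant who has so far received only 12 mg.

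The tables also leave it unclear whether the analysis is meant to run in 6.4.8 to 6.4.10, since the text carries it forward and Tables 12 to 15 do not list it. None of this removes the defect: if the rule is applied to an error after Day 1, it credits 12 mg time to the wrong group.

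**Conclusion.** The concern holds for the as-treated sensitivity analysis, and mainly for 50/28 mg versus 12 mg in 6.4.9 and 6.4.10. With no true effect the rule shifts the hazard ratio by about 2% for one wrong dose and 11% for five, on average towards the higher dose. Against sham the shift is at most about 0.03. The direction follows from the rule and the clock together. The size rests on assumed error counts, assumed event rates and an unstratified test, and it vanishes if there are no errors or only Day 1 errors. The documents do not support any claim that the ranked survival tests are biased. The rule is worth correcting before the analysis is run, because the correction is cheap and a robustness check should not have a built-in lean.

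**What to change.** - **Sections 6.4.9 and 6.4.10.** Keep a 12 mg participant's time in the 12 mg group until the first 50 or 28 mg dose, and count it as higher dose only from then on. Use treatment as a time-dependent term in the Cox model, or the equivalent log-rank test on split time. State the mirror case: a participant randomised to 50/28 mg who has received only 12 mg counts as 12 mg until the first higher dose.
- **Sections 6.4.7 and 6.4.8.** Do not add reclassified 12 mg participants to the Matched Sham Set comparison from Day 1.
- **Tables 12 to 15.** Add the as-treated analysis where it is intended, or remove it from the text, so that the two agree.

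The cost is a few sentences and table rows. No new data are needed, because section 5.5 already plans a listing of treatment actually received and of dosing errors. The small downside is that the sensitivity analysis will no longer be an exact repeat of the fixed-group log-rank test.

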## 6.4.8. Time to death (overall survival): comparison: 50/28mg versus CS3B sham control

Overall survival will be analyzed in the same way as time to death or permanent ventilation.

Analysis Method	Analysis Population: further notes
Log-rank test stratified by disease duration at Screening	Matched Sham Set
Cox proportional hazards with treatment and each subject's disease duration at Screening and baseline CHOP INTEND total score as terms in the model	Matched Sham Set
Log-rank test stratified by disease duration at Screening; by disease duration at Screening	Matched Sham Set
Log-rank test stratified by disease duration at Screening; by baseline CHOP INTEND total score.	Matched Sham Set
	
 
Log-rank test stratified by disease duration at Screening
 
Cox proportional hazards with treatment and each subject's disease duration at Screening and baseline CHOP INTEND total score as terms in the model
 
Log-rank test stratified by disease duration at Screening; by disease duration at Screening
 
Log-rank test stratified by disease duration at Screening; by baseline CHOP INTEND total
 

Table 13: Time to death: comparison: 50/28mg versus CS3B sham control

Product: Nusinersen	Statistical Analysis Pla	
Study: 232SM203	Version: 3.0 Final	

